#### Sample size

Sample size was estimated using free available calculator <http://www.quantitativeskills.com/sisa/calculations/samsize.htm>. Assuming an improvement of endothelial dysfunction of 30% (relative) and a SD of 3% (% FMD) a total of 42 subjects will be needed to detect this difference with an alpha of 0.05 and a power of 0.90. To account for a dropout rate of about 20% each group will consist of 25 patients.

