### **10.5 Withdrawal / Drop out of subjects**

Each subject has the right to withdraw from the study at any time without prejudice or compromise to future care.

The investigator may discontinue or withdraw the subjects under the following circumstances:

- Significant protocol deviation
- Significant non-compliance with treatment regime or study procedures
- An adverse event that requires discontinuation of the study medication or results in inability to continue to comply with study procedures. If a subject is withdrawn due to an adverse event, the investigator will arrange for follow-up visits or telephone calls until the adverse event has resolved or stabilised.
- Consent withdrawn
- Lost to follow up
- The study will be stopped prematurely if any information relating to the IMP or any other aspect of the study arises that may cause harm to the participant.
- Any other situation that may, in the opinion of the investigator, make it unsafe or inappropriate for the subject to continue in the trial

A drop-out rate of 10% was considered in the sample size estimate. In case of further drop-outs additional recruitment has to take place to avoid loss of statistical power.

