### **12.4 Data analysis and sample size estimation**

#### Data analysis

Continuous variables will be presented as means, standard deviation, median, minimum and maximum, for categorical data frequencies and relative frequencies are used. To examine differences between groups at baseline, t-tests or Mann-Whitney U tests and chi-square tests will be used as appropriate. The primary outcome, FMD after 12 weeks, will be analysed using ANCOVA. Comparisons within groups will be performed using paired t-test or Wilcoxon rank-sum test. A p-value of <0.05 is considered to indicate

statistical significance. A statistical analysis plan will be prepared and finalized before database lock.

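### The sample-size section and section 10.5 give different drop-out allowances (about 20% and 10%), and at 20% the 50 enrolled leave 40 evaluable, not the required 42

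*Protocol*

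**What the plan says.** The sample-size paragraph of section 12.4 assumes a 30% relative improvement and an SD of 3 (in % FMD), and concludes that "a total of 42 subjects will be needed to detect this difference with an alpha of 0.05 and a power of 0.90". It then sets enrolment: "To account for a dropout rate of about 20% each group will consist of 25 patients", which is 50 in total. It names an online calculator but gives no baseline or control FMD, no absolute difference, no formula and no sidedness.

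Section 10.5 describes the same estimate differently: "A drop-out rate of 10% was considered in the sample size estimate". It adds that drop-outs beyond this must be made up by further recruitment so that power is not lost.

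The data-analysis paragraph of section 12.4 names ANCOVA as the analysis of the primary outcome, FMD after 12 weeks.

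**The concern.** The two sections disagree on what the enrolment of 50 was meant to absorb. The 20% allowance in 12.4 does not protect the 42 evaluable subjects that the same paragraph requires; the 10% allowance in 10.5 does.

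This affects conduct as well as the record, because section 10.5 makes extra recruitment depend on the allowance. Whoever runs the trial cannot tell from the protocol whether the sixth or the eleventh loss calls for replacement. If it is the eleventh, the trial can end with fewer evaluable subjects than its own calculation asks for, with the protocol followed to the letter.

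**Working it through.** **Inputs.** From section 12.4: 42 evaluable in total (21 per arm), 50 enrolled (25 per arm), drop-out about 20%, alpha 0.05, power 0.90, 30% relative improvement, SD 3. From section 10.5: drop-out 10%. Assumed here because not stated: a two-sided test and the absolute difference.

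**Step 1: drop-out (no assumption needed).** Evaluable = enrolled × (1 − drop-out).

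- At 20%: 50 × 0.80 = 40, two below 42.
- At 10%: 50 × 0.90 = 45, three above 42.
- Enrolment needed to keep 42 at 20%: 42 / 0.80 = 52.5, so 53, or 54 for equal arms.
- Largest loss that 50 can absorb: 1 − 42/50 = 16%, or 8 subjects.

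Multiplying instead of dividing gives 42 × 1.2 = 50.4, which may explain the 50. The protocol does not show the step.

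**Step 2: recruitment trigger.** Ten per cent of 50 is 5 and twenty per cent is 10. Extra recruitment therefore starts after more than 5 losses (section 10.5) or more than 10 (section 12.4). On the second reading, 9 or 10 losses leave 41 or 40 evaluable with no trigger.

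**Step 3: reproducing the 42.** The stated inputs do not fix the absolute difference, so the standardised difference d has to be solved backwards from 42. Two reconstructions fit.

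- Normal approximation with d = 1 (3 points over SD 3, implying a baseline FMD of 10%): n per arm = 2 × (1.960 + 1.282)² / 1² = 21.01. Power at 21 per arm is 89.98%.
- Two-sample t-test with d = 1.025 (about 3.08 points, implying a baseline FMD of 10.25%): power at 21 per arm is 90.0%.

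**Step 4: power at 42 and at 40, two-sided alpha 0.05.**

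| Reconstruction | 42 evaluable | 40 evaluable |
|---|---|---|
| Normal approximation, d = 1 | 90.0% | 88.5% |
| t-test, d = 1.025 | 90.0% | 88.5% |
| t-test, d = 1 | 88.5% | 86.9% |

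Within each row, going from 42 to 40 costs about 1.4 to 1.6 percentage points.

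**Step 5: how far the missing baseline matters.** With a 30% relative improvement and SD 3, d = 0.30 × baseline / 3. Two-sided t-test power:

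| Assumed baseline FMD | d | 42 evaluable | 40 evaluable |
|---|---|---|---|
| 8% | 0.80 | 71.6% | 69.3% |
| 9% | 0.90 | 81.2% | 79.2% |
| 10% | 1.00 | 88.5% | 86.9% |
| 11% | 1.10 | 93.5% | 92.4% |
| 12% | 1.20 | 96.7% | 95.9% |

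**Step 6: the planned ANCOVA.** If SD 3 is the unadjusted week-12 SD and d = 1, adjusting for baseline FMD with correlation r raises the standardised difference to 1/√(1 − r²), at the cost of one degree of freedom. Power then reaches 90% at 42 evaluable when r is about 0.23 or more, and at 40 when r is about 0.32 or more. If SD 3 is already the residual SD, there is no further gain.

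**The case against.** Section 12.4 says about 20%, and 16% might pass for that. The gap is two subjects and costs roughly one and a half points of power. Section 10.5 provides for replacement, and if its 10% governs, recruitment resumes before the trial falls to 40. The planned ANCOVA is usually more efficient than the unadjusted comparison that the calculation appears to use, and a modest baseline correlation would restore 90% even at 40.

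Much of this stands, and it keeps the power loss small. It does not settle the contradiction. The protection from section 10.5 works only if 10% is the operative rate, and section 12.4 says it is not. The ANCOVA gain may well be real, but the calculation claims none, states no correlation and does not say which SD the 3 is.

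A reader might go further and infer that 90% is an arithmetic error: that it came from the normal approximation and that true power at 42 is 88.5%. The documents do not support that. The difference of 1 SD is not in the protocol; it is solved back from 42, so using it to show that 42 is wrong would be circular. A t-test at 1.025 SD also gives 90% at 42, and the calculator's method cannot be seen. Even at exactly 1 SD, the gap between the normal approximation and the t-test is only about 1.5 points. The 86.9% figure adds that change of test to the drop-out loss, and the t-test is not the planned analysis.

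**Conclusion.** Two points hold from the text alone. Fifty enrolled less 20% gives 40 evaluable, two short of the 42 required. Sections 10.5 and 12.4 also name different drop-out rates for one estimate, which leaves the recruitment trigger at either more than 5 or more than 10 losses.

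The effect on power is modest and conditional. Under either reconstruction that yields 90% at 42, power at 40 is about 88.5%; it is 86.9% if a t-test is applied to an assumed difference of exactly 1 SD. These figures assume a two-sided test and a difference that the protocol does not state. The missing baseline FMD is the larger uncertainty: between 8% and 12%, t-test power at 42 runs from 71.6% to 96.7%. No single power figure can be confirmed or refuted from the stated inputs. The inconsistency should be corrected, but it does not show the trial to be materially underpowered.

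**What to change.** 1. Use one drop-out rate in sections 10.5 and 12.4. Fifty enrolled supports 42 evaluable up to a 16% loss. If 20% is kept with 50 enrolled, give the expected evaluable number as 40.
2. Tie additional recruitment in section 10.5 to the expected evaluable number falling below the number required, not to a percentage. With 42 required and 50 enrolled, that is the ninth loss.
3. State in section 12.4 the baseline FMD, the absolute difference, the sidedness and what the SD of 3 refers to. A difference of 3 FMD percentage points should be written in only if the sponsor confirms it was the assumption used.
4. Restate power for the number expected to complete, either by t-test or by the planned ANCOVA with its assumed baseline to week-12 correlation. If SD 3 is unadjusted and the difference is 1 SD, a correlation of about 0.32 or more gives 90% at 40.

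The cost is wording in two sections, with no increase in the planned 50. The stated power may become slightly less favourable, or may rest on one added and visible assumption about the correlation.

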## **9. STUDY DESIGN**

This is a single-centre, prospective, randomized, double-blind, placebo-controlled, parallel group 12 week clinical trial evaluating the effect of Linagliptin 5mg OD orally on cardiovascular surrogate measures in patients with early diabetes. 50 subjects will be randomised to receive either Linagliptin or placebo for 12 weeks. At baseline all subjects will undergo endothelial function assessment (FMD), blood sampling as well as a meal tolerance test. At the end of the 12-week treatment period all subjects will undergo a repeat FMD, blood sampling as well as a meal tolerance test.

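### Sections 10.5 and 12.4 give different drop-out allowances (10% and about 20%) for the same sample size, and at 20% the planned 50 subjects leave 40, below the 42 required

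*Protocol*

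**What the plan says.** Protocol section 12.4 (Sample size) sets the evaluable number: "Assuming an improvement of endothelial dysfunction of 30% (relative) and a SD of 3% (% FMD) a total of 42 subjects will be needed", "with an alpha of 0.05 and a power of 0.90". It then moves to the number randomised: "To account for a dropout rate of about 20% each group will consist of 25 patients". Section 9 carries the resulting total: "50 subjects will be randomised to receive either Linagliptin or placebo for 12 weeks". The synopsis and section 10.1 also give 50.

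Section 10.5 describes the allowance differently: "A drop-out rate of 10% was considered in the sample size estimate". It attaches an action to it: "In case of further drop-outs additional recruitment has to take place to avoid loss of statistical power".

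The amendment history lists no change to the sample size or the drop-out rate, so nothing marks either statement as superseded.

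**The concern.** There are two faults. First, one calculation is given two drop-out rates, 10% and about 20%. Second, the rate in 12.4 does not lead from 42 to 50 when applied to the subjects randomised: losing 20% of 50 leaves fewer than the 42 the same paragraph asks for.

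The rate would matter little if it only explained where 50 came from. Section 10.5, however, makes it the threshold beyond which recruitment must resume to protect power. With two rates in the protocol, that rule has no single trigger. Under the 20% reading it starts only after the evaluable count has already fallen below 42. A team following that reading could finish with 40 evaluable subjects and still regard the planned 90% power as preserved. A team could also settle on a reading only once drop-outs have accrued, so the final number randomised is not fixed beforehand.

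**Working it through.** **Inputs.** From 12.4: alpha 0.05 (sidedness not stated), power 0.90, SD 3% FMD, relative improvement 30%, 42 evaluable in total (21 per group), drop-out about 20%, 25 per group. From 10.5: drop-out 10%, with extra recruitment beyond it. From section 9: 50 randomised.

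**1. The figure of 42.** For two independent means with the normal approximation, n per group = 2 × (z₁₋α/₂ + z_power)² × SD² / Δ². The protocol gives no reference FMD, so Δ has to be assumed. With a two-sided test and Δ = 3 points:

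- 2 × (1.960 + 1.2816)² × 9 / 9 = 21.01 per group, 42.03 in total. This matches 42; strict rounding up would give 22 per group (44).
- Solving backwards from 21 per group: Δ = 3 × √(2 × (1.960 + 1.2816)² / 21) = 3.001 points. As a 30% relative change, this implies a mean FMD of 3.001 / 0.30 = 10.0%.
- A one-sided test at Δ = 3 gives 17.13, so 18 per group (36), which does not match.

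The implied mean FMD is undisclosed, not shown to be wrong. The steps on drop-out below take 42 as stated.

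**2. From 42 to 50.** If a fraction d of those randomised is lost, N randomised = N evaluable / (1 − d).

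| d | 42 / (1 − d) | Per group, 21 / (1 − d) | Equal groups, total |
|---|---|---|---|
| 10% | 46.7 | 23.3 → 24 | 48 |
| 16% | 50.0 | 25.0 → 25 | 50 |
| 20% | 52.5 | 26.25 → 27 | 54 |

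Neither stated rate gives 50. Multiplying instead of dividing does: 42 × 1.2 = 50.4. That is probably how 50 arose. The loss that 50 actually covers is (50 − 42) / 50 = 8/50 = 16%.

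**3. Evaluable subjects and power.** Power is at a difference of 1 SD (Δ = 3, SD = 3), two-sided 0.05, with no credit for ANCOVA.

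| Loss from 50 | Evaluable | Power, normal approximation | Power, t-test |
|---|---|---|---|
| 10% | 45 | 0.918 | 0.906 |
| 16% | 42 | 0.900 | 0.885 |
| 20% | 40 | 0.885 | 0.869 |

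Going from 42 to 40 costs about 1.5 points of power.

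**4. When the rule in 10.5 starts.**

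- 10% of 50 = 5 allowed: recruitment resumes at the 6th drop-out, with 44 left.
- Protecting 42: 50 − 42 = 8 allowed, so the 9th drop-out, with 41 left.
- 20% of 50 = 10 allowed: the 11th drop-out, with 39 left.

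**The case against.** The strongest reply is that the consequence is slight. The rate in 12.4 is approximate, and the margin of 8 subjects is 19% of the 42 needed (8/42), so the authors may simply have expressed it on that base. Under the 10% in 10.5 there is no shortfall at all, since 45 would remain. The primary analysis is an ANCOVA. If it adjusts for baseline FMD and the SD of 3% is a raw week-12 SD (both assumptions), 40 subjects match an unadjusted 42 once 1 − r² = 40/42, that is, at a baseline-to-outcome correlation of about 0.22. Section 10.5 also states its purpose as protecting power, and 12.4 says what power needs, so a sensible reader could infer a top-up below 42. Replacement based on pooled drop-out counts in a double-blind trial uses no treatment effect and does not threaten the type I error.

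Most of this stands as a limit on severity. The power loss is small and may be offset by ANCOVA, and no bias is claimed. It does not remove the fault. No reading of about 20% agrees with 10%. The top-up rule cannot repair the discrepancy, because its trigger is the figure in dispute. Inferring 42 as the threshold means reading past the rates that both sections actually state.

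**Conclusion.** The concern holds. The two sections contradict each other on the drop-out allowance, and 50 randomised fits neither rate: it leaves 45 at 10% and 40 at 20%, and meets 42 only up to a 16% loss. These results need only the protocol's own 42 and 50.

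The effect on power is minor, 0.900 falling to 0.885 (t-test 0.885 to 0.869). Those values assume a two-sided, two-sample comparison at a 1 SD difference without covariate adjustment. The more important effect is operational: the recruitment trigger lies anywhere from the 6th to the 11th drop-out, and the latest reading acts only after the required number is already lost. This should be corrected, but it does not undermine the design.

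**What to change.** State one drop-out rate in 10.5 and 12.4 and tie extra recruitment to the evaluable count. The smallest change keeps 50. Both sections would say that the sample allows for up to 16% drop-out (8 of 50), leaving 42 evaluable. If more than 8 subjects in total, counted without regard to arm, have no week-12 FMD, further subjects are randomised until 42 are evaluable. Pooled counting keeps the rule independent of allocation. Its weakness is an uneven split: if all 8 losses fell in one arm, 25 + 17 would be equivalent to 2 × 25 × 17 / 42 = 20.2 per group, with power about 0.889, roughly one point lower.

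If the sponsor does expect 20% loss, the number randomised should be 54 wherever 50 now appears.

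In the same edit of 12.4, give the target as an absolute FMD difference (3.0 points if the calculation was two-sided and two-sample), the mean FMD assumed, what the SD of 3% refers to, and the sidedness of alpha.

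The cost is one sentence in 10.5 and one paragraph in 12.4. No extra patients are needed if 16% is stated, and four more are randomised if the 20% allowance is kept.

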### **13 TREATMENT/INTERVENTION**

#### *Study Treatment/Intervention*

- Placebo
- Linagliptin

#### **13.1 Description of Treatments/Interventions**

The subjects will receive either Linagliptin 5mg (licensed dose for treatment of type 2 diabetes) or matched placebo tablets orally once daily for 12 weeks. The drug and placebo will be supplied by Böhlinger Ingelheim as bulk ware study medication. Pharmacy at the Medical University of Graz, Austria will pack the medication as 12 weeks supplies for study participants and label study medication according to current regulatory requirements.

Patients will be asked not to adjust their antidiabetic treatment during the study period. However, if glycaemic control appears to be inappropriately high during these 12 weeks, additional glucose lowering drugs may be used at the discretion of the principal investigator. Unless contraindicated, the first choice for rescue medication should be a sulfonylurea.

### **13.2 Subject Compliance**

The subjects will be instructed to return all unused or part-used medication and packaging from medication at the follow-up visit. Tablets will be counted out at the end of the twelve week treatment period to verify compliance.

Significant non-compliance is defined as missing 20% or more doses of trial medication during the 12 week treatment period. In the event of study medication non-compliance, participants would continue to be followed to their last visit. These data would not be part of the per protocol analysis but would form part of an intention to treat analyses.

## **14 INVESTIGATIONAL MEDICINAL PRODUCT (TAKEN FROM THE SMPC)**

### **14.1 Mechanism of action**

Linagliptin is an inhibitor of the enzyme DPP-4 (Dipeptidyl peptidase 4, EC 3.4.14.5) an enzyme which is involved in the inactivation of the incretin hormones GLP-1 and GIP (glucagon-like peptide1, glucose-dependent insulinotropic polypeptide). These hormones are rapidly degraded by the enzyme DPP-4. Both incretin hormones are involved in the physiological regulation of glucose homeostasis. Incretins are secreted at a low basal level throughout the day and levels rise immediately after meal intake. GLP-1 and GIP increase insulin biosynthesis and secretion from pancreatic beta cells in the presence of normal and elevated blood glucose levels. Furthermore GLP-1 also reduces glucagon secretion from pancreatic alpha cells, resulting in a reduction in hepatic glucose output. Linagliptin binds very effectively to DPP-4 in a reversible manner and thus leads to a sustained increase and a prolongation of active incretin levels. Linagliptin glucose-dependently increases insulin secretion and lowers glucagon secretion thus resulting in an overall improvement in the glucose homeostasis. Linagliptin binds selectively to DPP-4 and exhibits a > 10,000 fold selectivity versus DPP-8 or DPP-9 activity in vitro.

### **14.2 Therapeutical indications**

Linagliptin is indicated in the treatment of type 2 diabetes mellitus to improve glycaemic control in adults:

as monotherapy

-in patients inadequately controlled by diet and exercise alone and for whom metformin is

inappropriate due to intolerance, or contraindicated due to renal impairment.

as combination therapy

-in combination with metformin when diet and exercise plus metformin alone do not provide adequate glycaemic control.

-in combination with a sulphonylurea and metformin when diet and exercise plus dual therapy with these medicinal products do not provide adequate glycaemic control.

### **14.3 Undesireable effects**

In the pooled analysis of the placebo-controlled trials, the overall incidence of adverse events in patients treated with placebo was similar to linagliptin 5 mg (53.8% versus 55.0%). Discontinuation of therapy due to adverse events was higher in patients who received placebo as compared to linagliptin 5 mg (3.6% versus 2.3%). The most frequently reported adverse reaction was hypoglycaemia observed under the triple combination, linagliptin plus metformin plus sulphonylurea 14.7% versus 7.6% in placebo.

In the placebo controlled studies 5.0% of patients experienced "hypoglycaemia" as an adverse reaction under linagliptin. 86.8% of these were mild and 13.2% were moderate.

### **14.4 Absorption**

The absolute bioavailability of linagliptin is approximately 30%. Co-administration of a high-fat meal with linagliptin prolonged the time to reach Cmax by 2 hours and lowered Cmax by 15% but no influence on AUC 0-72h was observed. No clinically relevant effect of Cmax and Tmax changes is expected; therefore linagliptin may be administered with or without food.

### **14.5 Distribution**

As a result of tissue binding, the mean apparent volume of distribution at steady state following a single 5 mg intravenous dose of linagliptin to healthy subjects is approximately 1110 litres, indicating that linagliptin extensively distributes to the tissues. Plasma protein binding of linagliptin is concentration-dependent, decreasing from about 99% at 1 nmol/l to 75-89% at ≥30 nmol/l, reflecting saturation of binding to DPP-4 with increasing concentration of linagliptin. At high concentrations, where DPP-4 is fully saturated, 70-80% of linagliptin was bound to other plasma proteins than DPP-4, hence 30-20% were unbound in plasma.

#### **14.6 Excretion**

Following administration of an oral [C] linagliptin dose to healthy subjects, approximately 85% of the administered radioactivity was eliminated in faeces (80%) or urine (5%) within 4 days of dosing. Renal clearance at steady state was approximately 70 ml/min.

## 15 PHARMACOVIGILANCE

Safety endpoints: All adverse events reported by the patients will be assessed and reported as outlined below.

### 15.1 Definitions

#### *Adverse Events (AE)*

An adverse event is defined as

any untoward medical occurrence, including an exacerbation of a pre-existing condition, in a patient or clinical investigation subject administered a pharmaceutical product. The event does not necessarily have to have a causal relationship with this treatment (Linagliptin).

#### *Adverse Drug Reaction (ADR)*

An Adverse Drug Reaction (ADR) is any response to a drug which is noxious and unintended.

This means that a causal relationship between study medication and an AE is at least a reasonable possibility i.e. the relationship cannot be ruled out.

